0.1 Objective

To assess the impact of uric acid production inhibitors (xanthine oxidase inhibitors) and uric acid excretion enhancers (uric acid transporter URAT 1 inhibitors) on renal function decline in patients with chronic kidney disease (CKD) complicated by hyperuricemia and hypertension.

0.2 Target population

Patients with CKD stage 3a-3b with hyperuricemia and hypertension

0.3 Study design

Multicenter, randomized, parallel two-arm study

0.4 Study schedule

Run in period (Visit1): 8 weeks of life guidance begins

Treatment phase 1 (Visit 2) Group A: Lifestyle guidance + URAT 1 inhibitor (benzbromarone)

Group B: Lifestyle guidance + xanthine oxidase inhibitor (febuxostat)

Start of administration

(Visit 3) 8 weeks after starting drug administration

Treatment phase 2: same drug as treatment phase 1 for another 44 weeks

Visit 4: 52 weeks after starting medication

0.5 Study drugs

Xanthine oxidase inhibitor: febuxostat (Feburic® Tablets)

URAT 1 inhibitor: benzbromarone (Urinorm® tablet)

0.6 Endpoints

(1) Primary endpoints

Percentage and absolute change in eGFR at 52 weeks (1 year) from the value immediately before the start of drug administration

(2) Secondary endpoints

1) Percentage and absolute change in eGFR at Week 8 after initiation of treatment

2) Percentage and absolute change in office blood pressure at 8 & 52 weeks after initiation of treatment

3) Difference in percent Percentage and absolute change in eGFR at 8 & 52 weeks before and after initiation of treatment

4) Percentage and absolute change in serum uric acid level and rate of attainment of serum uric acid level below 6.0 mg/dL at weeks 8 & 52 after initiation of treatment

5) Percentage and absolute change in urinary albumin/creatinine ratio at weeks 8&52 after initiation of treatment (%)

6) Percentage and absolute change in urine pH at 8&52 weeks after initiation of treatment

7) Percentage and absolute change in XO activity at 8&52 weeks post-dose initiation

8) Percentage and absolute change in hs-CRP at 8&52 weeks after initiation of treatment

9) Percentage and absolute change in urinary 8-OHdG (8-hydroxy-2'-deoxyguanosine) at weeks 8 & 52 after initiation of treatment

10) Percentage and absolute change in urinary angiotensinogen at weeks 88&52 after initiation of treatment

11) Proteinuria for the primary endpoint, stratified analysis by renal function

1. Background

The prevalence of hyperuricemia in Japanese adult males is thought to be as high as 30% after the age of 30 and is still rising.¹ 1) Hyperuricemia is linked to the occurrence and progression of chronic kidney disease (CKD). Epidemiological studies have demonstrated that serum uric acid level is a risk factor for the development of CKD and that there is a strong correlation between serum uric acid level and the deterioration of renal function.²⁻⁴ Particularly, the association between uric acid and CKD has been demonstrated to be common in hypertensive patients.⁵ Because the risk of end-stage renal failure and cardiovascular disease rises with the progression of CKD,^{6, 7} intervention for hyperuricemia in hypertensive patients with CKD may not only prevent renal function decline but also improve patient prognosis.

Studies using an animal hyperuricemia model have shed light on the mechanism underlying CKD progression by hyperuricemia. Uric acid-induced-renal microvascular lesions are thought to play a key role in the development of hypertension and renal damage.^{8,9} Inflammation, oxidative stress,

and the renal renin-angiotensin system have been also proposed as potential contributors to the mechanism of microvascular lesions.¹⁰ According to our research, hyperuricemia affects renal microvascular lesions in CKD patients without regard to other comorbid conditions like hypertension or diabetes mellitus.¹¹ Renal arteriolar lesions may aid in the progression of renal damage through glomerular hypertension and ischemia, two common mechanisms of renal damage. They may also aid in the development of cardiovascular disease by raising blood pressure.

Several prospective interventional trials have reported that xanthine oxidase (XO) inhibitors, which reduce uric acid production, prevent GFR decline in CKD patients. Urate transporter 1 (URAT1) is expressed on the cell membrane of vascular cells and has all been suggested to be linked to intracellular oxidative stress, inflammation, and uric acid-induced enhancement.^{12, 13} Therefore, URAT1 inhibitors are anticipated to improve renal microvascular lesions and slow the development of CKD. It is currently unknown whether the reduction of uric acid itself, inhibition of XO activity, or inhibition of URAT1 causes the inhibition of CKD progression.

Febuxostat, an XO inhibitor with a novel mechanism of action, is a uric acid-lowering drug that was authorized for the treatment of gout and hyperuricemia in Japan in January 2011. Clinical trials have demonstrated that febuxostat has excellent serum uric acid-lowering abilities and it is effective and safe in patients with mild to moderate renal dysfunction,¹⁴ and the approval of febuxostat broadens treatment options for hyperuricemia. Benzbromarone received approval in August 1978 to treat hyperuricemia brought on by gout and hypertension. It reduces hyperuricemia by specifically preventing uric acid reabsorption in the tubules (URAT 1 inhibition) and encouraging uric acid excretion into the urine.

In this parallel-group study, we will evaluate the effects of febuxostat and benzbromarone on eGFR and the effects of blood pressure, urinary albumin excretion, XO-active oxidative stress, inflammatory markers, and renal RA system markers of hypertensive patients with chronic kidney disease and hyperuricemia

2. Objective

To assess how febuxostat and benzbromarone affect renal function in CKD patients with hyperuricemia and hypertension

3. Target population

3.1 Target Patients

Patients with CKD stage 3a-3b with hyperuricemia and hypertension

3.2 Inclusion criteria

Patients who meet the following criteria shall be included (1) through (7) at the time of eligibility determination.

- ① Serum uric acid level greater than 7.0 mg/dL
- ② Hypertension (untreated patients with an office blood pressure of 140/90 mmHg or higher or on antihypertensive medication) who have not changed their antihypertensive medication for 8 weeks before the eligibility determination
- ③ CKD stage 3a-3b
- (4) Age 20 years or older at the time of obtaining consent
- (5) Outpatients
- 6) Patients with no history of gout
- (7) Patients who have given their written informed consent to participate in the study.

[Rationale]

- ① The definition of hyperuricemia was set following the definition of hyperuricemia in the Guidelines for the Treatment of Hyperuricemia and Gout (2nd edition)¹⁶.
- ② An association between hyperuricemia and the progression of CKD has been prevalent in patients with hypertension. (Ref)
- ③ Urate lowering therapy is a favor for slowing the decline in eGFR in CKD patients.
- ④ The subjects were adults. The upper limit of age was not set to examine the significance in actual clinical practice.
- ⑤ The study was limited to outpatients with relatively stable medical conditions.
- (6) This was set in consideration of the need for drug treatment based on the treatment

guidelines for hyperuricemia and gout [1].

(7) Participation in the study was set because it was based on the free will of the patients themselves.

3.3 Exclusion Criteria

If any of the following items (1) through (13) are violated at the time of eligibility determination, the company shall be excluded from the scope.

- ① History of hypersensitivity to the drugs used
- ② AST or ALT is more than twice the institutional standard value
- ③ Severe renal dysfunction (eGFR less than 30 mL/min./1.73m² or more than 60 mL/min./1.73m², dialysis patients)
- ④ Under medication with thiazide diuretics, loop diuretics
- ⑤ Under medication with urate lowering drugs in the 2 weeks before an eligibility determination
- ⑥ Patients who developed coronary artery disease within 3 months before an eligibility determination
- ⑦ History of malignancies (unless the malignancy has been untreated for at least 5 years since the time of eligibility determination and is judged not to have recurred)
- ⑧ Patients receiving any of the following drugs
Mercaptopurine hydrate, azathioprine, pyrazinamide, ethambutol
- ⑨ Under medication with warfarin
- ⑩ Patients who are lactating, pregnant, or may be pregnant
- ⑪ Patients who have participated in other clinical studies (including clinical trials) within 6 months before an eligibility determination
- ⑫ Urinary tract stones
- ⑬ Other patients whom the physician in charge judges to be unsuitable as subjects.
- ⑭ Patients with serum uric acid levels below 7.0 mg/dl in the post-visit 2 lifestyle guidance phase will not be randomized to the treatment phase. (Final eligibility check)
- ⑮ Patients with a history of acute myocardial infarction, acute coronary syndrome, coronary artery stenosis intervention (catheterization and coronary artery bypass surgery), ventricular tachycardia, multisource ventricular arrhythmia, or acute heart failure within 3 months before the time of eligibility determination (newly added based on the results of the CARES study)

[figure not shown]
[Rationale]

Febuxostat is contraindicated in patients receiving the drugs listed in ⑧. It may potentiate the effect of warfarin.

4. Research plan

4.1 Design of the study

1 Design of the study

4.2 Expected number of participants and implementation period

Expected number of participants: 100 (50 in each of treatment groups A and B)

Research period: After approval by the Ethical Review Committee - February 28, 2021

Research registration period: After approval by the Ethical Review Committee - November 30, 2018

The basis for setting the number of expected participants.

We predicted that a sample size of 100 participants the study would provide 90% power to detect differences in the primary outcome (change in eGFR) of 15 mL/min/1.73m² per year between the randomized groups based on the findings of previous studies,^{14, 15} assuming a standard deviation of 20 mL/min/1.73m², a drop-out rate of 20%, a type I error rate of 5%, and the use of a two-sided significance test.

4.3 Case Registration and Assignment Methods

After verifying the eligibility of the candidate patients and obtaining their written consent to participate in the study, the physician in charge creates a case registration form and submits it to the research secretariat for case registration. The research secretariat will verify the case registration form's information. Additionally, the research secretariat will fill out the reply column on the case registration form with the eligibility determination results and, if applicable, the allocation results (treatment group A or treatment group B), and then return it to the physician in charge.

The research office members in charge of allocation will generate random numbers to distribute assignments according to an allocation table they have created. The research secretariat's person in charge of allocation will be the only one with knowledge of and strict control over the allocation table. The allocation factors will be determined using the data at the time of eligibility confirmation, which will include the following four items: age 70 years or older, gender, percentage of patients with CKD stage 3b, and presence of urinary albumin of 300 mg/gCr or higher.

4.4 Details of the research treatment

The attending physician will begin the research treatment depending on the results of the allocation.

(1) Run in period

During the Run in phase (8 weeks), lifestyle advice (diet, alcohol consumption restriction, exercise recommendations, etc.) will be given regarding the Guidelines for the Treatment of Hyperuricemia and Gout (2nd edition)¹⁶.

(2) Treatment period 1

Following final eligibility determination, febuxostat 10 mg/day or benzborbromarone 25 mg/day will be administered in treatment phase 1 after confirming tolerability, along with lifestyle recommendations. The daily dosage of febuxostat will be increased to 20 mg/day beginning in week 5. Treatment should last for 8 weeks.

(3) Treatment period 2

A serum uric acid level of less than 6 mg/dl should be attained by adjusting the medication used in treatment phase 1. The recommended course of treatment is 44 weeks (1 year from the start of the drug).

If gouty arthritis appears during the observation period, the dosage of benzborbromarone, and febuxostat should be continued without modification in principle. For benzborbromarone, use Urinorm® tablets, and Feburic® tablets for febuxostat.

4.5 Combination therapy

In principle, the type, dosage, or administration of concomitant medications should not be changed during Treatment Periods 1 and 2. However, this does not apply to cases where intensification of treatment is required because of deteriorating renal or blood pressure function, or where changes in treatment are necessary to address other complications. Patients

receiving benz bromarone should be advised to drink water, and urine alkalinization should be considered if the patient's urine is acidic.

4.6 Notification to other departments and hospitals

The treating physician will determine if the patient is visiting another department or hospital. If the subject is visiting another department or hospital, the head doctor and the subject's attending doctor at the other department or hospital will be notified of the subject's participation in this study.

4.7 Completion, discontinuation, and suspension of study

(1) Criteria for completion of study

Subjects will be discontinued from the study if any of the following occur

a) Ineligibility as a subject

- (1) If it is discovered after the study has begun that the subject was ineligible for inclusion and exclusion requirements, etc.
- (2) If it is discovered after the research has begun, the patient's circumstances or other factors make it impossible to continue conducting the required observations (examinations).
- (3) If it comes to light that you are pregnant or think you might be.

If the uric acid level falls to less than 3 mg/dl following the start of administration

b) The subject's offer (withdrawal of consent)

If a subject case requests to discontinue participation in the study after it has begun

c) Transfer to another hospital

If the study's subject case is moved to a different hospital after it begins

d) clinical development

- (1) If the subject passes away following the start of the research
- (ii) If, following the start of the research, the subject becomes unable to follow the protocol due to cardiovascular complications (onset or worsening of heart failure, acute myocardial infarction, cerebrovascular accident, new onset of peripheral arterial disease, or the introduction of renal replacement therapy).

e) Discontinuation due to the onset of adverse events

If adverse events, etc. make it impossible to follow the implementation plan

f) Other

When the in-charge doctor determines that the research should be stopped.

(2) Procedure for discontinuing the research

If the subject is determined to fall under the discontinuation criteria, the physician in charge will explain this and stop the research.

If a safety issue, such as the occurrence of an adverse event, requires the study to be terminated, the responsible physician will take prompt appropriate measures and, in theory, will continue to monitor the patient until recovery or until it is decided that additional investigation is not required.

If it is discovered after the study has begun that the subject is unable to travel to the hospital due to circumstances, etc., the subject's health will be confirmed by telephone, etc., along with the reason for the absence and safety of the subject will be confirmed.

The physician in charge of cases where the research has been stopped should detail the date of discontinuation, the reason for discontinuation, the processing, observations up to Visit 3 (week 8), and Visit 4 (week 52), even after discontinuation for potential cases, test results that can be gathered, and subsequent progress in the case report form.

5. survey items and schedule

5.1 Schedule

The responsible doctor will conduct observations and examinations according to the following schedule. The results should be described in the case report.

	Run in period (Visit 1) ^{*3}	Treatment phase 1 (short-term effects)		Treatment phase 2 (long-term effects)		
		Visit2 ^{*4}	Visit3	Just before the start	8 weeks later	52 weeks later
Subject background		●				
Height ^{*1} , weight, abdominal circumference ^{*1}		●	●	●	●	
Blood pressure, pulse rate		●	●	●	●	
AST, ALT, TC ^{*5} , LDL ^{*5} , HDL ^{*5} , TG ^{*5} , serum uric acid, HbA1c, GLU, serum creatinine ^{*2}	● ^{*3}		●	●	●	
Na, K, Cl						
Plasma XO Activity			●	●	●	
Inflammatory Markers			●	●	●	
Oxidative Stress Markers			●	●	●	
Urinary angiotensinogen			●	●	●	
Urinary L-FABP			●	●	●	
urinalysis	●	●	●	●	●	
Medication status of research drugs				●	●	
Concomitant medications			●	●	●	
adverse event						→

^{*1} Height and abdominal circumference can be measured once during the study participation period.

^{*2} Calculate eGFR using the estimation formula of the Japanese Society of Nephrology.

^{*3} Test results within 4 weeks before the time of eligibility determination shall be made available.

Visit 3 test results will be available within 2 weeks before and after the test.

Visit 4 test results will be available within 4 weeks before and after the test.

After final eligibility confirmation, serum uric acid levels below 7.0 mg/dl will not be entered into the treatment phase.

If there is no value measured by a medical institution, the value is automatically calculated by a formula:

$$TC-HDL-C-(TG/5)=LDL-C$$

5.2 Survey items

(1) Background of subjects

The following items shall be investigated when determining eligibility.

Age, gender, CKD stage, blood pressure, renal function, pre-existing conditions, and complications

(2) Height, weight, and abdominal circumference

Weight will be measured when determining eligibility, before the start of each treatment period, and after each treatment period. Height will be measured once during the study participation period. Concurrent pharmaceuticals (antihypertensive agents, diuretics, antidiabetic agents, lipid agents, basic renal failure agents)

(3) Blood pressure and pulse rate

At the time of eligibility determination, before the start, and after each treatment period, blood

pressure, and pulse rate will be checked after resting in a sitting position for 5 minutes.

(4) Blood test, renal function

The following items will be measured when determining eligibility determination, Run period, and moments before, 8W after, and 52W after initiation of therapeutic agents. When determining eligibility, test results from 4 weeks before the time of eligibility determination will be available for the determination.

AST, ALT, TC, LDL, HDL, TG, serum creatinine, Na, K, Cl, serum uric acid, HbA1c, GLU
Calculate the eGFR using the following formula13).

eGFR (mL/min/1.73m²)=194 x Cr^{-1.094} x Age^{-0.287} (x 0.739 for women)

(5) Plasma XO activity

Measurements will be taken shortly before the start of therapeutic agents, 8W after the start, and 52W after the start. For measurement, samples are frozen at -80°C, and batch measurement is conducted when the number of samples is available.

(6) Inflammatory markers, oxidative stress markers, renal RA system markers, and tubulointerstitial damage markers

Measurements will be taken shortly before therapeutic agents begin, 8W after the start, and 52W after the start. Samples will be frozen at -80°C for measurement, and batch measurement will be conducted when the number of samples is adequate. Among the following items, inflammatory markers, oxidative stress markers, and urinary L-FABP will be assessed by SRL Co.

Inflammatory markers: high sensitivity CRP

Oxidative stress markers:

Urinary 8-OHdG (8-hydroxy-2'-deoxyguanosine)

Urinary angiotensinogen

Urinary L-FABP

(7) Urinalysis (microalbuminuria and urine pH, urine Na, urine UA)

(Early morning) Use urine as needed. (Early morning) Use urine as needed.

(8) Inspection for safety confirmation

In addition to the aforementioned, AST, ALT, serum creatinine, Na, K, Cl, serum uric acid, and urinalysis will be conducted on each outpatient clinic day from 8W to 52W to track the side effects of hepatic and renal disorders.

(9) Compliance with research treatment

After each treatment period, the subjects will be questioned about the study drugs' medication status in the following four stages.

(1) I almost took it (more than 90%)

(2) Sometimes forgot to take the medication (more than 70% to less than 90%)

(iii) More than half of them took it (more than 50% to less than 70%)

④ Less than half of the patients took the drug (less than 50%)

(10) Concomitant medications

No drug modifications will be made during the Run in phase and Treatment phase 1 if possible. The types and daily doses of antihypertensive drugs, diuretics, antidiabetic drugs, lipid drugs, and basic renal failure drugs until the conclusion of the study will be evaluated.

(11) Adverse events

Assess adverse events during study participation

(12) Data collection

Data collection will be performed by a clinical research coordinator affiliated with the implementing medical institution or the researcher's institution.

[figure not shown]
6. Overview of the research agent

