4.1. Handling of follow-up survey results

Survey will be conducted at initiation of run-in period (visit 1), immediately before initiation of randomized treatment (visit 2), and 8 & 52 weeks after initiation of treatment (visits 3 & 4). Visit 3 survey results within 2 weeks of the planned visit will be used for statistical analysis and visit 4 survey results within 4 weeks of the planned visit will be used for statistical analysis. When participants are complicated with concomitant disease which can affect eGFR, survey results after onset of the disease will be deleted as missing values.

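### No on-treatment laboratory test is scheduled between the first dose and Visit 3 (week 8), including around the febuxostat increase from week 5 (cheap improvement)

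*Protocol*

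**What the plan says.** **Testing.** Protocol section 5.2, item (4), covers AST, ALT, creatinine, electrolytes and uric acid. Besides the eligibility and run-in tests, blood is taken "moments before, 8W after, and 52W after initiation of therapeutic agents". Item (8) adds a clinic-day panel with a stated purpose and a stated period: "urinalysis will be conducted on each outpatient clinic day from 8W to 52W to track the side effects of hepatic and renal disorders". Section 5.1 sets the window for the first visit on drug: "Visit 3 test results will be available within 2 weeks before and after the test". Section 4.1 of the statistical analysis plan text bound with the protocol lists the same on-study time points: "immediately before initiation of randomized treatment (visit 2), and 8 & 52 weeks after initiation of treatment (visits 3 & 4".

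**Dosing.** Under section 4.4, febuxostat 10 mg/day or benzbromarone 25 mg/day "will be administered in treatment phase 1 after confirming tolerability". Then: "The daily dosage of febuxostat will be increased to 20 mg/day beginning in week 5". No test, time or threshold is attached to either sentence.

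**Stopping.** Section 4.7 ends participation "If the uric acid level falls to less than 3 mg/dl following the start of administration". It also allows stopping for adverse events and, under f), "When the in-charge doctor determines that the research should be stopped".

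**Known risks.** Section 6.2 lists hepatic dysfunction as a serious reaction for both drugs. The benzbromarone excerpt adds fulminant hepatitis, and its Note 2 says to stop the drug for liver reactions, a row that includes AST and ALT rises. The febuxostat excerpt lists abnormal liver tests and raised creatinine.

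**The concern.** The clinic-day panel exists to follow hepatic and renal side effects, yet its stated period leaves out the weeks in which both drugs are first taken and one is doubled. A rise in AST, ALT or creatinine without symptoms can be seen only by a test. The same is true of a uric acid value below 3 mg/dL, although that stopping rule applies from the start of administration. Before Visit 3, no scheduled result can reveal any of these. What is at stake is earlier detection in individual patients. The comparison between the arms is not at issue.

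**Working it through.** The plan gives no figure for this point, so there is none to reproduce. The check sets dosing times against test times. The schedule table in section 5.1 is damaged in extraction, so the running text of sections 0.4, 4.4, 5.1 and 5.2 is used.

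| Time | Dosing | Scheduled laboratory test |
|---|---|---|
| Visit 2 | just before first dose | blood panel, item (4) |
| First dose to the week-5 step | febuxostat 10 mg or benzbromarone 25 mg | none |
| Week-5 step to Visit 3 | febuxostat 20 mg or benzbromarone 25 mg | none |
| Visit 3, week 8 (6 to 10) | end of period 1 | blood panel, item (4) |
| Weeks 8 to 52 | adjusted towards uric acid below 6 mg/dL | item (8), each clinic day |
| Visit 4, week 52 | end | blood panel, item (4) |

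Scheduled on-drug tests before the febuxostat step: 0. First scheduled on-drug test: week 8, or week 6 at the earliest.

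**Length of the interval.** 8/52 = 15.4%. With the two-week window: (8 − 2)/52 = 11.5% to (8 + 2)/52 = 19.2%.

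**Time on febuxostat 20 mg before the first on-drug test.** The step can be read as coming after 4 or after 5 completed weeks. Nominal: 8 − 4 = 4 or 8 − 5 = 3 weeks. With the window: 6 − 5 = 1 to 10 − 4 = 6 weeks.

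**Exposure.** 100 patients × 8 weeks = 800 patient-weeks (100 × 6 = 600 to 100 × 10 = 1,000). This restates the schedule and does not measure harm.

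**Uric acid rule.** From the 7.0 mg/dL entry floor, reaching 3 mg/dL needs a fall of (7.0 − 3.0)/7.0 = 57.1%, and more from a higher start. The documents give no rate for this.

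**Liver-test abnormalities (assumption).** The benzbromarone table gives only 0.1% or more for AST and ALT rises, and its hepatic dysfunction has unknown frequency. The febuxostat table prints a band for abnormal liver tests whose heading is garbled; I read it as 1% to under 5%. The period to which these rates apply is not stated. I take them as 52-week rates, with 50 patients per arm and 8/52 of events falling in the interval if onset is even.

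| Assumed rate | Patients per arm in 52 weeks | In the interval, even onset |
|---|---|---|
| 0.1% | 50 × 0.001 = 0.05 | 0.05 × 8/52 = 0.008 |
| 1% | 50 × 0.01 = 0.5 | 0.5 × 8/52 = 0.08 |
| 5% | 50 × 0.05 = 2.5 | 2.5 × 8/52 = 0.38 |

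Febuxostat falls in the last two rows. For benzbromarone only the 0.1% floor is printed; 1% and 5% are assumed. If all onset were early, the middle column would apply instead.

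**Effect of a named week-4 test.** The longest nominal interval without a test in period 1 falls from 8 weeks to 4 (weeks 0 to 4, then 4 to 8). With Visit 3 at week 10 it falls from 10 weeks to 10 − 4 = 6.

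**The case against.** The strongest reply is that the schedule has a logic. Each drug starts at the lowest tablet strength listed in section 6.1, period 1 has one fixed febuxostat step, and open-ended dose adjustment begins in period 2, just when clinic-day testing starts. Both drugs are marketed and used within approved doses. Adverse events are assessed throughout, tolerability must be confirmed, and the physician may test or stop at any time. Section 6.1 also refers to product documents that are not shown and may specify early monitoring.

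All of that stands as mitigation, and it keeps the point minor. It does not supply a scheduled test. The tolerability wording names none, adverse-event assessment is not a laboratory check, and the claim concerns only what this protocol itself schedules.

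A second reply is that starting the clinic-day panel earlier guarantees nothing, because no clinic day is defined between Visits 2 and 3. This also stands, and the fix below says so.

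A reader might infer more than the documents support:

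- *No laboratory check at all before the febuxostat increase.* Not so: the Visit 2 panel is taken just before the first dose, and section 3.3 excludes AST or ALT above twice the institutional standard.
- *The uric acid stopping rule is inoperative.* Not so: it works at Visit 3, later, and on any unscheduled value.
- *The protocol breaks its own liver stopping rule.* Note 2 is a label excerpt without a threshold and is not among the section 4.7 criteria.
- *The statistical analysis plan confirms a lack of safety testing.* Its section 4.1 governs which survey results enter the analysis. It agrees with the visit schedule but is not separate evidence on safety tests.
- *The eGFR endpoint or the serious adverse event comparison is biased.* Nothing in the documents shows this.

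**Conclusion.** The point holds as a cheap improvement, graded minor. The protocol schedules no on-treatment laboratory test between the first dose and Visit 3, in either arm, for a nominal 8 weeks (6 to 10). That interval contains the start of both drugs and the febuxostat doubling. The schedule follows directly from the text of section 5.2. It is a matter for the protocol and not for the analysis plan, because item (8) fixes week 8 as its starting point.

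The size in patients is uncertain and probably small: under even onset, below 0.4 abnormal liver tests per arm at a 5% yearly rate, and up to 2.5 if all were early. These figures rest on assumed rates and on my reading of a damaged table heading. The document also carries result tables, so the point concerns the plan as written.

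**What to change.** 1. In section 5.2, item (8), start the clinic-day panel at the start of drug instead of week 8, keep week 52 as the end, and apply it in both arms.
2. Add one sentence: at any clinic day at about week 4, AST, ALT, creatinine and uric acid are reviewed, before the febuxostat increase in that arm, with the same testing in the benzbromarone arm.
3. State that these results act only through the existing section 4.7 routes (uric acid below 3 mg/dL, adverse events, the physician's decision) and do not enter the eGFR endpoints.

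Cost: a wording change, an added sentence, up to about one extra routine panel per patient (0 to 100 panels if each patient has at most one clinic day before Visit 3), and possibly a few earlier discontinuations. No new visit is required, and sample size and endpoints do not change. Patients with no clinic day before Visit 3 gain nothing. To cover everyone, the sponsor would have to name a week-4 test, which means one panel for each patient and an added attendance for those not otherwise due.
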